In this context, systems biology approaches offer a new approach to compare the global architecture of the immune response between PPV23 and PCV13. Systems biology is a biologybased inter-disciplinary study field that focuses on complex interactions in biological systems, using a new holistic perspective. Systems biology offers several so-called "Omic" technologies that can provide unbiased and rich information on the physiological state of organisms through their molecular profiles. These systems biology approaches are likely to be of value in identifying molecular signatures that are induced rapidly after vaccination and that correlate with, and predict, the later development of protective immune responses. Such a strategy would be particularly useful when evaluating the efficacy or immunogenicity of suboptimal vaccines, or in identifying individuals who are likely to respond sub-optimally to vaccination, such as the elderly receiving PPV23 in particular. Furthermore, the predictive signatures would highlight new correlates of protective immunity and stimulate the formulation and validation of new hypotheses on the biological mechanisms by which such molecular signatures modulate vaccine-induced immunity and protection. Despite this promise in identifying molecular signatures, they have only recently been applied to vaccinology^{10, 11}.

Accordingly, a key goal of the present proposal is to identify molecular signatures that predict the sub-optimal immunogenicity of PPV23 when compared to PCV13 in the elderly. One of the

CONFIDENTIAL

key systems biology technologies that will be employed are microarray analyses. Essentially, blood samples will be isolated at baseline (day 0 prior to vaccination), and at days 1, 3, 7, 14 post vaccination, and the RNA from the peripheral blood mononuclear cells isolated and analyzed for the expression of mRNAs. The microarray platform will be Affymetrix Human Genome U133 Plus 2.0 Array, similar to what we had used previously¹⁰. In our previous work on yellow fever vaccine¹⁰, we identified a gene signature that correlates with and predicted YF-17D CD8+ T cell responses with up to 90% accuracy in an independent, trial. A distinct signature, including B cell growth factor TNFRS17, predicted then neutralizing antibody response with up to 100% accuracy. These findings highlight the utility of system biology approaches in predicting vaccine efficacy.

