1.7 Benefits

1.7.1 Benefits of Investigational Product(s)/Intervention(s)

Participants will have the benefit of receiving a licensed pneumococcal vaccine which may offer protection against pneumococcal disease. Also the knowledge gained from this study could facilitate the design of more effective pneumococcal vaccines for the geriatric population.

1.7.2 Benefits of Study Procedure(s)

None

2. **OBJECTIVES**

PCV13 induces better functional immune responses when compared to PPV23 in older naïve adults. We hypothesize that this is due to intrinsic defects in innate responses that could explain the poor immunogenicity of PPV23 when compared to PCV13. Therefore, we propose to extensively study innate and adaptive immune responses generated after administration of either pneumococcal polysaccharide or conjugate vaccines in older adults.

2.1 **Primary Objective(s)**

To analyze the generic innate immune signatures that correlate with the magnitude of the adaptive immune responses (opsonophagocytosis [OPA] titers) at day 30 in order to identify the correlation signatures of the innate immune responses to PPV23 and PCV13.

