3.1 Study Endpoints

3.1.1 Primary Endpoint(s)

- 3.1.1.1 Identification of generic innate immune signatures [Traditional immune parameters measurements + array-based gene expression] at days 1, 3 and 7 post vaccination with either PPV23 or PCV13 in the elderly.
- 3.1.1.2. Measurement of adaptive immune responses [Opsonophagocytosis assay (OPA) titers] at day 30 post vaccination with either PPV23 or PCV13 in the elderly.
- 3.1.1.3. Correlation of signatures of generic innate immune responses at days 1, 3 and 7 with adaptive immune responses [Opsonophagocytosis assay OPA titers] at day 30 post vaccination with either PPV23 or PCV13 in the elderly.

3.1.2 Secondary Endpoint(s)

- 3.1.2.1. Comparison of serotype specific IgG levels at day 30 post vaccination with either PPV23 or PCV13 in the elderly.
- 3.1.2.2. Correlation of signatures of generic innate immune responses at days 1, 3 and 7 that correlate to serotype specific IgG levels at day 30 post vaccination with either PPV23 or PCV13 in the elderly.
- 3.1.2.3. Comparison of the serotype specific avidity indexes in a subset of up to 6 vaccinees per vaccine group at day180 post vaccination with either PPV23 or PCV13 in the elderly.

- 3.1.2.4. Correlation signatures of generic innate immune responses at days 1, 3 and 7 that correlate to serotype specific avidity indexes in a subset of up to 6 vaccinees per vaccine group at day 180 post vaccination with either PPV23 or PCV13 in the elderly.
- 3.1.2.5. Comparison of the adaptive immune responses [Opsonophagocytosis assay (OPA) titers] at day 30 post vaccination with either PPV23 or PCV13 in the elderly.

3.1.3 Exploratory Endpoint(s)

3.1.3.1. Identification of correlation signatures of generic innate immune responses at days 1, 3 and 7 that correlate to adaptive immune responses [Opsonophagocytosis assay OPA titers specifically] at day 30 post vaccination among subjects in different age strata.

3.1.3.2. Comparison of the kinetics and magnitude of select serotype specific plasmablasts (days 7, 14, 30(with day 30 on a subset of vaccinees only)) and memory B cells (days 30, 180) post vaccination with either PPV23 or PCV13.

3.1.3.3. Comparison of the repertoire and monoclonal antibodies from plasmablasts in a subset of vaccinees per vaccine group at day 7 post vaccination with either PPV23 or PCV13.

3.1.3.4. Comparison of identified innate signature variables and correlation signature variables between PPV23 and PCV13 recipients.

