9. SAMPLE SIZE CALCULATIONS AND STATISTICAL PLAN

9.1. Sample Size and Power Calculations

The study is explorative. Not enough preliminary data exists to support accurate calculation of the sample size. However we conducted a sample size analysis based on hypothetical scenarios and knowledge of similar studies. Based on previous studies performed at the Hope Clinic and the Vaccine Research Trials Center, the rate of subjects that become ineligible during the study (i.e. do not meet exclusion/inclusion criteria anymore, lost to follow-ups, unable to have blood draws) is between 5 to 10%. Assuming 10% attrition rate, 88 subjects will be recruited and 1:1 randomized into the two treatment groups, resulting in an expected 80 subjects for data analysis. The sample size is on-par with similar studies. In the case that the sample size of subjects missing any of the 4 draws required for the primary endpoint [meaning draws at days 1, 3, 7(\pm 1), and 30 (\pm 7)] is higher than 10% of the 88 subjects to be recruited for the study, we will recruit extra patients to maintain the target sample size of 80 subjects.

The randomization process will be detailed in the MOP. At the center of this study is the identification of generic innate signatures and finding their correlations with the adaptive immune response. The generic innate signatures will be identified from both traditional immune parameters measured by FACS/Luminex assays and array-based gene expression will be measured by microarray experiments. The generic innate signatures will be identified for different treatment groups separately. The traditional immune parameters and array-based gene expression that change after immunization are considered generic innate signatures. The traditional immune parameters and array-based gene expression that change after immunization are considered generic innate signatures. The traditional immune parameters and array-based gene expression that are correlated with the adaptive immune responses (day 30 OPA titers, day 30 IgG levels, day 180 serotype specific avidity indexes, plasmablasts also) are considered correlation signatures of the innate immune responses.

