9.2. Data Analysis

9.2.1. General considerations

The young treatment groups are of limited size. The main purpose of the young treatment groups is to provide some indication whether the elderly respond to the vaccines differently than the young. By themselves, the young groups do not have sufficient statistical power to generate reliable innate and correlation signatures. However when used in comparison against elderly groups, and by only considering biological pathways (collections of genes contributing to the same biological process) that are affected by the vaccine, they can provide some indication as to how different the response is in the elderly compared to the young. Thus for data analysis, the young treatment groups will be used only in exploratory endpoints. The primary and secondary endpoints will focus on the elderly groups.

The analyses will be based on population with critical time points met, defined as those who received vaccine per label and got the 4 draws required for the primary endpoint, i.e. draws at days 1, 3, 7 (\pm 1), and 30 (\pm 7) within the required windows. Data from the study will be analyzed using the statistical software R³¹. High-throughput data will be analyzed using appropriate methods, either by stand-alone software or modules in leading statistical softwares, e.g. the Bioconductor in the R framework³². For cytokine data, missing values will be dealt with using multiple imputations. For microarray data, nearest neighbor method and local least squares may be used to fill missing values. Unsupervised learning techniques such as PCA, PLSDA, clustering, and factor analysis ³³ will be used for the visualization and identification of global patterns. For descriptive endpoint (primary endpoint 2), we will generate summary statistics, and visualize the data using histograms and boxplots when applicable. For the identification of innate signatures, the two treatment groups will be analyzed separately.

Analyses of primary endpoints:

1. Identification of generic innate immune signatures [Traditional immune parameters measurements + array-based gene expression] at days 1, 3 and 7 post vaccination with either PPV23 or PCV13 in the elderly.

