The innate signatures will be detected in each elderly treatment group separately. We will take the measurements on the day of vaccination as baseline. For traditional immune parameters, we will test if an immune parameter shows significant change over baseline at day 1, 3, and 7 after each vaccination, using a two-sided paired t-test. In addition, for each immune parameter, the fold-change over baseline will be calculated for every subject. The average (arithmetic mean) fold change over the 30 subjects will be combined with the test p-value in a selection criterion as appropriate. Based on previous studies similar in nature, the tentative selection criterion is pvalue ≤ 0.01 and average fold change ≥ 3 .

For the gene expression data, again the innate signatures will be detected in each elderly treatment group separately. We will use the method Significance Analysis of Microarrays (SAM) ³⁴ with paired design to find differentially expressed genes over the baseline. False discovery rate (FDR) will be used as selection criterion. The tentative selection criterion is FDR \leq 0.1.

2. Measurement of adaptive immune responses [Opsonophagocytosis assay (OPA) titers] at day 30 post vaccination with either PPV23 or PCV13 in the elderly.

The OPA titers will be presented as descriptions of the actual values separately in both study elderly populations (PPV23 and PCV13 recipients). Summary statistics, boxplots and histograms will be used to summarize the data.

3. Correlation of signatures of generic innate immune responses at days 1, 3 and 7 that correlate to adaptive immune responses [Opsonophagocytosis assay OPA titers] at day 30 post vaccination with either PPV23 or PCV13 in the elderly.

The correlation signatures will be detected in each elderly treatment group separately. The innate signature markers/genes identified in Primary Endpoint 1 will be used in this step for the identification of correlation signature.

For traditional immune parameters, we will calculate the correlation coefficient between the immune parameter and the adaptive immune response (day 30 OPA titers). The p-values associated with the correlation coefficients will be used to select traditional immune parameters

that are associated with the respective adaptive immune responses (day 30 OPA titers). The tentative selection criterion is p-value ≤ 0.01 .

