Appendix 2. Definitions

"Generic innate immune signatures"=traditional immune parameters measurements + arraybased gene expression, which change in response to vaccination.

« Traditional immune parameters » = FACS + Luminex.

« FACS »= Fluorescence Activated Cell Sorting, a method for sorting a heterogeneous mixture of biological cells.

« Luminex »= multiplex analysis technique for measuring of cytokines and chemokines

"Array-based gene expression" =microarray.

"Adaptive immune responses" = OPA + avidity indexes+ ELISA IgG+ studies on plasmablasts.

"Correlation innate immune signatures" =traditional immune parameters measurements + array-based gene expression, which correlate with adaptive immune responses.

"Gene ontology": a set of standard terminology that group gene products based on their biological functions.

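### A day-7 marker that tracks day-30 OPA cannot be attributed to innate rather than adaptive cells, yet the plan would report it as an innate correlate

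*Combined protocol and SAP*

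**What the plan says.** Section 9.2.1 defines primary endpoint 1 as "Identification of generic innate immune signatures [Traditional immune parameters measurements + array-based gene expression] at days 1, 3 and 7 post vaccination", in the elderly, with each vaccine group analysed separately. Days 1, 3 and 7 have the same status.

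The label depends on change alone. Section 9.1 states: "The traditional immune parameters and array-based gene expression that change after immunization are considered generic innate signatures". Appendix 2 gives the same definition, covering FACS, Luminex and array variables "which change in response to vaccination". Neither place sets a condition on cell type, lineage or gene set.

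The selected markers feed primary endpoint 3, the correlation with day-30 OPA: "The innate signature markers/genes identified in Primary Endpoint 1 will be used in this step for the identification of correlation signature".

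Plasmablasts are on the adaptive side. Appendix 2 defines the adaptive response as "OPA + avidity indexes+ ELISA IgG+ studies on plasmablasts", and section 3.1.3 plans a "Comparison of the kinetics and magnitude of select serotype specific plasmablasts (days 7, 14, 30(with day 30 on a subset of vaccinees only". The plasmablast repertoire and monoclonal antibody work is also on day 7. The Appendix 1 footnote rules out adaptive assays at day 1 and innate assays at days 30 and 180, so day 7 carries both families.

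Section 1.1 says the array RNA comes from peripheral blood mononuclear cells. It describes no sorting or B-cell depletion.

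**The concern.** The study hypothesis is mechanistic. Section 2 says of the better functional response to PCV13 than to PPV23 in older adults: "We hypothesize that this is due to intrinsic defects in innate responses". The primary objective looks for innate correlates of OPA as evidence on that hypothesis.

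On day 7 the array sample can contain antibody-secreting B-lineage cells. A transcript from those cells that rises from baseline and tracks day-30 OPA would satisfy every rule for a correlation signature of the innate response, with no innate cell involved. The same holds for a FACS marker that counts B-lineage cells, if the panel has one (the panel is not listed). Luminex cytokines are less directly exposed.

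What is at stake is what a positive day-7 finding means. It could be reported as support for the innate-defect hypothesis when it shows only that an early adaptive response goes with a later antibody titre. Secondary endpoints 2 and 4 use the same labels for IgG and avidity, and exploratory endpoint 4 carries them into the vaccine and age comparisons.

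**Working it through.** **Step 1. The plan's own figures.** Section 9.1 gives 80% power with 30 subjects per elderly arm for r = 0.57 at alpha 0.01 (immune parameters) and r = 0.60 at alpha 0.005 (genes), two-sided. Fisher approximation: power = Φ(atanh(r)·√(n−3) − z(1−α/2)).

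- r = 0.57: atanh = 0.6475; × √27 = 3.365; minus 2.576 gives Φ(0.789) = 78.5% (simulation 79.5%).
- r = 0.60: atanh = 0.6931; × √27 = 3.602; minus 2.807 gives Φ(0.795) = 78.7% (simulation 79.6%).

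Both agree with the stated 80% within two points. The arithmetic of the plan is sound; the question is what a day-7 hit represents.

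**Step 2. The chain of rules for a plasmablast transcript at day 7.**

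| Rule | Source | Met? |
|---|---|---|
| Measured by array, FACS or Luminex | Appendix 2 | Yes |
| Taken at day 1, 3 or 7 | 3.1.1, 9.2.1 | Yes |
| Changes from baseline | 9.1, 9.2.1 | Yes, if the cells rise |
| Correlates with day-30 OPA | 9.2.1, primary endpoint 3 | Yes, if plasmablasts do |
| Not of adaptive origin | No such rule | Not tested |

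**Step 3. An illustration of size.** The documents give no correlation between plasmablasts and OPA, so both inputs are assumptions: the gene correlates l = 0.8 to 0.9 with day-7 plasmablasts, and plasmablasts correlate ρ = 0.5 to 0.7 with log OPA. With no other path, the induced correlation is r = l × ρ. At n = 30 and alpha 0.005:

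| l | ρ | r | Fisher | Simulation |
|---|---|---|---|---|
| 0.8 | 0.5 | 0.40 | 27% | 27% |
| 0.9 | 0.6 | 0.54 | 63% | 64% |
| 0.9 | 0.7 | 0.63 | 85% | 86% |

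Chance alone would give 0.5%. With wider assumptions (l 0.7 to 1.0, ρ 0.4 to 0.8) the Fisher range is 9% to over 99%.

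These are probabilities for a gene that has already passed the change-from-baseline step. They use the planning alpha; the actual gene analysis is SAM with a tentative FDR of 0.1 or less.

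**Step 4. Would adjusting for plasmablasts separate the two?** Two models with the same l and ρ, n = 30, alpha 0.005, using the partial correlation given plasmablasts:

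| Marker | Unadjusted | Adjusted, plasmablasts measured without error |
|---|---|---|
| Pure plasmablast gene, no innate content | 27% to 86% | about 0.5% |
| Truly innate marker acting wholly through plasmablasts | 27% to 86% | about 0.5% |

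The two rows match because the covariance structure is the same. If the plasmablast measure has an assumed reliability of 0.3 to 0.5, the adjusted test still passes the pure plasmablast gene in 7% to 64% of cases. Section 3.1.3 plans an assay of selected serotype-specific plasmablasts, whereas RNA from unsorted cells would reflect all plasmablasts, so imperfect reliability is plausible. Adjustment therefore cannot decide which markers are innate.

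**The case against.** The strongest reply is that *innate signature* is an explicit operational term. Section 9.1 and Appendix 2 tell the reader that it means variables that change after vaccination. Section 1.1 also wants early signatures that predict later responses, and a day-7 predictor of OPA serves that aim whatever its lineage. The tests and error rates are unaffected. This stands as far as it goes: the problem is one of construct and interpretation. It does not rescue the hypothesis in section 2, which uses *innate* in the mechanistic sense.

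A second reply is that the plan has partial safeguards. Change is tested at days 1, 3 and 7, so the earlier days can be read without day 7. Section 9.2.1 also foresees pathway enrichment with biological interpretation, which could expose B-cell content. Both are true. But neither limits the claim made from day 7, and the pathway work is exploratory.

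A reader might infer more than the documents support:

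- *That a day-7 correlate is simply the antibody response correlated with itself.* Day-7 cells and a day-30 functional titre are different measurements, and the marker may still be innate. The documents show only that its origin is undetermined.
- *That 27% to 86% of such trials would report a false innate correlate.* That range depends on assumed correlations, the planning alpha and a gene already past the first step.
- *That the investigators' earlier yellow fever work already shows the effect.* Section 1.1 says: "A distinct signature, including B cell growth factor TNFRS17, predicted then neutralizing antibody response with up to 100% accuracy". It gives neither a sampling day nor a plasmablast origin for that gene, so it makes the concern plausible and no more.

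**Conclusion.** The concern holds for day 7 only. Followed exactly, the plan can report a plasmablast transcript, or a B-lineage FACS marker, as an innate correlate of OPA on the primary objective, and it has no rule by which to tell that case from a true innate one. This conclusion comes from the definitions and the assay schedule and needs no numerical assumption.

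Its frequency cannot be computed from the documents. Under the assumed loadings and correlations above, the correlation step would select a pure plasmablast gene far more often than chance. Days 1 and 3 are not called into question, and neither are the plan's power figures. The change is a cheap improvement that matters because it alters what the trial can conclude about its innate-defect hypothesis.

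**What to change.** In primary endpoints 1 and 3, secondary endpoints 2 and 4 and Appendix 2 (with the matching definition in section 9.1):

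1. Keep the terms *innate signature* and *innate correlation signature* for days 1 and 3.
2. Run the same tests with the same criteria at day 7, but report them separately as an *early (mixed innate/adaptive) response signature*.
3. State that a day-7 finding does not by itself support the innate-defect hypothesis.
4. If results adjusted for day-7 serotype-specific plasmablasts are shown, present them as descriptive only. They should not decide whether a marker is innate: adjustment also removes true innate effects mediated by plasmablasts, and the assay is an incomplete proxy for all plasmablasts in the sample.

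The cost is wording and a narrower claim at day 7. No sample, assay or test is added or lost.

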In summary the proposed study offers an unprecedented opportunity to capture the global architecture of immune responses to PPV23 versus PCV13 in the elderly. This is likely to have a major impact in two areas: (i) the elucidation of unique signatures of innate immune response that predict vaccine immunogenicity, and will thus be relevant from a public health perspective; (ii) such unique signatures of innate immune response may illuminate the immunologic defects responsible for sub-optimal immunity in the elderly population when using a polysaccharide vaccine when compared to a conjugate vaccine.

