For gene expression data, we will use the method Significance Analysis of Microarrays (SAM) with quantitative outcome to identify genes that are significantly associated with the respective adaptive immune responses (day 30 OPA titers). False discovery rate (FDR) will be used as selection criterion. The tentative selection criterion is FDR ≤ 0.1 .

Analyses of secondary endpoints:

1. Comparison of the serotype specific IgG levels at day 30 post vaccination with either PPV23 or PCV13 in the elderly.

Descriptive analysis, boxpots and histograms, will be conducted to present the data. Testing between the two elderly treatment groups will be conducted using unpaired t-test after proper data transformation. In the case that near-normality cannot be achieved with data transformation, we will resort to the Wilcoxon test.

2. Correlation of signatures of generic innate immune responses at days 1, 3 and 7 with serotype specific IgG levels at day 30 post vaccination with either PPV23 or PCV13 in the elderly.

The analysis will be conducted in each elderly treatment group separately. For traditional immune parameters, we will calculate the correlation coefficient between the immune parameter and the adaptive immune response (IgG levels at day 30 post vaccination). The p-values associated with the correlation coefficients will be used to select traditional immune parameters that are associated with the respective adaptive immune responses (IgG levels at day 30 post vaccination). The tentative selection criterion is p-value ≤ 0.01 .

For gene expression data, we will use the method Significance Analysis of Microarrays (SAM) with quantitative outcome to identify genes that are significantly associated with the respective adaptive immune responses (IgG levels at day 30 post vaccination). False discovery rate (FDR) will be used as selection criterion. The tentative selection criterion is $FDR \le 0.1$.

3. Comparison of the serotype-specific avidity indexes in a subset of up to 6 vaccinees per vaccine group at day 180 post vaccination with either PPV23 or PCV13 in the elderly.

Descriptive analysis, boxpots and histograms, will be conducted to present the data. Testing between the two elderly treatment groups will be conducted using unpaired t-test after proper data transformation. In the case that near-normality cannot be achieved with data transformation, we will resort to the Wilcoxon test.

CONFIDENTIAL

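### Primary Endpoint 3 and Secondary Endpoint 2 prespecify no Day-0-adjusted analysis, so the planned within-arm Day 30 correlation does not separate correlates of pre-existing antibody from correlates of vaccine response

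*Combined protocol and SAP*

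**What the plan says.** Objective 2.1 looks for innate signatures that "correlate with the magnitude of the adaptive immune responses (opsonophagocytosis [OPA] titers) at day 30". Its stated purpose is to "identify the correlation signatures of the innate immune responses to PPV23 and PCV13". Endpoint 3.1.1.3 correlates the innate signatures "with adaptive immune responses [Opsonophagocytosis assay OPA titers] at day 30 post vaccination".

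Section 9.2.1 carries this out separately in each elderly arm:
- **Immune parameters (Primary Endpoint 3):** "we will calculate the correlation coefficient between the immune parameter and the adaptive immune response (day 30 OPA titers"), selected at p ≤ 0.01.
- **Genes (Primary Endpoint 3):** "we will use the method Significance Analysis of Microarrays (SAM) with quantitative outcome to identify genes" associated with the same titers, selected at FDR ≤ 0.1.
- **Secondary Endpoint 2:** the correlation is "between the immune parameter and the adaptive immune response (IgG levels at day 30 post vaccination"), with the same two thresholds.

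No covariate, partial correlation, fold rise or sensitivity analysis using Day 0 OPA or IgG is specified. In 9.2.1 the day-of-vaccination value serves as baseline only for detecting change in the innate markers (Primary Endpoint 1). Secondary Endpoints 1 and 5 compare Day 30 IgG and OPA between arms by unpaired t-test, or Wilcoxon if transformation fails.

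The background in section 1.1 describes the expected yield as "the elucidation of unique signatures of innate immune response that predict vaccine immunogenicity" and states that "a key goal of the present proposal is to identify molecular signatures that predict the sub-optimal immunogenicity of PPV23".

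**The concern.** A Day 30 level reflects what the vaccine induced and what was there before. Section 4.2 excludes prior pneumococcal vaccination but sets no antibody limit at entry, and section 9.2.3 records earlier pneumococcal disease as a baseline characteristic. Subjects may therefore differ in antibody at Day 0. A marker that varies with that antibody can correlate with the Day 30 level and be selected, even if it has nothing to do with the response to vaccination.

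Two features of the design do not remove this. Randomization balances the arms, but each correlation is computed inside one arm. The Primary Endpoint 1 filter (only markers that change after vaccination go forward) limits how many markers are exposed, not the selection rate for each one, since the change itself may depend on existing antibody.

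What is at stake is interpretation: a marker of prior exposure could be reported as a marker of vaccine immunogenicity, which is the use section 1.1 has in mind.

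**Working it through.** **Inputs from the documents.** 30 per elderly arm, two-sided alpha 0.01 and detectable correlation 0.57 for immune parameters; alpha 0.005 and correlation 0.60 for genes (section 9.1).

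**1. The plan's own power figure.** Critical |r| = t/√(df + t²) with t = 2.763 and df = 28, giving 0.463. By Fisher's z with the bias term r/(2(n−1)):
- atanh(0.57) + 0.57/58 = 0.6475 + 0.0098 = 0.6573
- atanh(0.463) = 0.5010
- (0.6573 − 0.5010) × √27 = 0.812, so power is 79.2%

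The same method gives 79.0% for 0.60 at alpha 0.005. Both agree with the stated 80%.

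**2. Selection of a marker linked only to Day 0 antibody.** All inputs here are assumed, and none is in the documents. Log values are bivariate normal. Let b be the Day 0 log titer, y = ρb + √(1−ρ²)e the Day 30 log titer, and m = cb + √(1−c²)u the marker. Given b, m and y are unrelated, but their plain correlation is c × ρ. Simulated selection rates at p ≤ 0.01, n = 30, 400,000 trials per cell:

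| Marker–Day 0 correlation c | ρ = 0.3 | ρ = 0.5 | ρ = 0.7 |
|---|---|---|---|
| 0 | 1.0% | 1.0% | 1.0% |
| 0.1 | 1.1% | 1.2% | 1.5% |
| 0.2 | 1.4% | 2.1% | 3.2% |
| 0.3 | 1.8% | 3.6% | 6.9% |
| 0.5 | 3.6% | 10.4% | 24.9% |

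With Day 0 partialled out (critical |r| 0.471, df 27) the rate is 1.0% in every cell, provided Day 0 is measured without error. At an assumed Day 0 reliability of 0.6 the adjusted rate is about 1.5% (c = 0.3, ρ = 0.5), 2.4% (0.5, 0.5) and 5% (0.5, 0.7). The effect on gene selection by SAM at FDR ≤ 0.1 was not quantified.

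**3. Power cost of adjusting.** If Day 0 is unrelated to both marker and outcome, simulated power at correlation 0.57 goes from 79.4% to 77.5%. If a marker with total correlation 0.57 shares variance with Day 0, its partial correlation is (0.57 − cρ)/√((1−c²)(1−ρ²)):

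| c, ρ | Partial correlation | Adjusted power at 0.01 |
|---|---|---|
| 0.3, 0.5 | 0.42/0.826 = 0.51 | 62% |
| 0.5, 0.5 | 0.32/0.75 = 0.43 | 40% |
| 0.5, 0.7 | 0.22/0.618 = 0.36 | 25% |

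The unadjusted power is about 79% in each row.

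**4. Arm comparisons (Secondary Endpoints 1 and 5).** Assume two-sided 0.05, 30 per arm and a difference d = 0.736 SD, which gives 80% power by unpaired t-test (noncentrality 0.736 × √15 = 2.85, df 58). ANCOVA changes the effective difference to d/√(1−ρ²) with df 57. Simulated power is 83%, 89% and 97% at ρ = 0.3, 0.5 and 0.7. At ρ = 0 it moves from 80.1% to 79.4%.

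**5. Is Day 0 available?** In Appendix 1 the blood-draw row listing IgG ELISA and OPA is marked at Day 0, and the footnote drops adaptive assays only at Day 1. Section 9.2.2 requires a Day 0 sample. Section 9.2.1 lists the required draws as Days 1, 3, 7 and 30, without Day 0. The two population definitions do not match.

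**The case against.** The strongest reply is that the plan analyses what it names. Objective 2.1 sets the Day 30 magnitude as the target. The phrase about the two vaccines qualifies the innate responses, which are tested for change from Day 0. The immunogenicity statements are background, not rules for interpreting section 9, and predicting a Day 30 titer does not require removing Day 0. The study also calls itself explorative, its thresholds are tentative, and section 9.4 allows further analyses ad hoc.

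Much of this stands. A reader might infer that the Day 30 correlation is wrong, or that the study could never separate the two explanations. Neither follows: the correlation is right for its named target, and Day 0 values appear obtainable. What remains is that no such analysis is prespecified, although correlation signatures are at the center of the study and Objective 2.2 speaks of adaptive responses to the vaccines. An ad hoc analysis carries less weight than one fixed beforehand.

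A second reply also stands. It is tempting to call a marker a vaccine correlate only if it is significant after adjustment. Step 3 shows that this would discard most markers with genuine partial correlations of 0.43 or 0.36, with 30 per arm.

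**Conclusion.** The omission is certain from the text; its importance is not. With a marker to Day 0 correlation of 0.1 to 0.2, the selection rate is 1.1% to 3.2% against a nominal 1%. It exceeds 10% only in the cells where that correlation is 0.5 and the Day 0 to Day 30 correlation is at least 0.5, and it reaches about 25% at 0.5 and 0.7. These figures rest on assumed correlations, normal logs and 30 per arm, and they cover immune parameters only.

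Two further inferences are not supported. The power figures in section 9.1 are sound for the correlations they describe. Secondary Endpoints 1 and 5 are not biased by leaving out Day 0, since they compare randomized arms; the loss there is precision. Nor would adjustment give full control if the Day 0 titer carries measurement error or a detection floor.

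A prespecified adjusted analysis beside the planned one is a worthwhile change at low cost.

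**What to change.** 1. Keep the Day 30 correlation as the primary analysis.
2. For Primary Endpoint 3 and Secondary Endpoint 2, prespecify a Day-0-adjusted analysis beside it, per serotype or for a summary score defined in advance. For immune parameters, use the partial correlation given log Day 0, rank-based if near-normality fails. For genes, use SAM with log Day 30 and the gene measure both residualized on log Day 0. Fold rise alone is not a safe substitute: under assumed equal Day 0 and Day 30 variances, it selected the marker linked only to Day 0 in 2% to 39% of simulated trials.
3. Report both estimates with confidence intervals for every selected marker. Describe a marker whose association shrinks markedly as possibly reflecting pre-existing antibody; do not require adjusted significance.
4. In Secondary Endpoints 1 and 5, replace the unpaired t-test with ANCOVA of log Day 30 on arm and log Day 0, or a rank-based version.
5. Confirm that OPA and IgG are run on the Day 0 sample, since Appendix 1 lists all assays in one combined row. Add Day 0 to the required draws in 9.2.1 to match 9.2.2.

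**Cost.** SAP wording, one covariate per serotype or score, a second set of results and no new blood draw. If the Day 0 assays are not already planned, they would have to be run on the stored sample. The adjusted correlation loses about 2 points of power when Day 0 is irrelevant and much more when marker and Day 0 overlap, which is why it belongs beside the planned analysis and not in place of it.
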